Subjects were randomized in double-blind, counterbalanced, placebo-controlled fashion to either placebo or a single 200mg dose of tolcapone on their first visit and the alternative treatment on their second visit. After receiving task instructions and undergoing a brief practice session of 10-20 trials, subjects performed the delay discounting task (Figure 1) within the MRI scanner while blood-oxygen level dependent (BOLD) images were obtained. Subjects entered the MRI scanner 90 minutes after drug ingestion to ensure that the delay discounting task was performed while drug levels were at peak (approximately 120 minutes: tolcapone package insert, Valeant Pharmaceuticals). The 256 total trials were presented in pseudorandom order. At the start of each trial, subjects were cued to one of four trial types: Want (W), Don't Want (DW), Sooner (S), and Larger (L) (see below). For each of these trial types, subjects were then presented with two hypothetical alternatives: a smaller amount of money available today ("Now") and a larger amount available later ("Later"). We have previously shown that this paradigm with hypothetical rewards effectively engages subjects (Boettiger et al., 2007; Boettiger et al., 2009), consistent with reports that hypothetical rewards activate common brain regions involved in value computations (Kang et al., 2011). As in our previous work (Boettiger et al., 2007), the 'Later' option consisted of six amounts (\$1, \$2, \$5, \$10, \$20, or \$100) at one of five future delays (1 week, 2 weeks, 1 month, 3 months, or 6 months). The percentage difference between the Now and Later options was selected from one of four different values (30%, 15%, 10%, and 5%). Subjects then made a button press to select one of the two options, randomly assigned to

the left and right sides of the screen.

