Each of the four trial types allowed us to investigate different functions. In the W condition, the primary analytic focus of this study, subjects chose the option they preferred. In the DW condition, subjects also chose the option they preferred, but then made a button-press to select the opposite choice. This condition permitted us to evaluate motor impulsivity by comparing the proportion of responses in the W and DW conditions. In the S and L conditions, which we combined to form a control (CON) condition, subjects simply selected the sooner or larger options, respectively. These trial types allowed us to ensure that subjects were appropriately following instructions, and to introduce a condition in which the decision about monetary options was not a motivated choice. The W condition comprised half of all trials; the CON conditions comprised one-third; and the DW condition comprised one-sixth. As expected, subjects performed very well in the CON condition (accuracy = 0.97 ± 0.008 (sem)) and therefore we do not further report results of the CON condition in this paper.

The primary behavioral outcome was the impulsive choice ratio (ICR), which represents the ratio of the number of sooner choices to the number of total choices in the W condition. As in our previous work, we calculated a number of related measures of impulsive choice, including a measure of the hyperbolic discounting rate (k) and the interest rate differentiating the two choices. Because values such as the hyperbolic discounting rate were highly correlated with ICR (e.g. $r(\text{ICR}, k) = 0.78$, $p < 1 \times 10^{-5}$) and consequently gave qualitatively similar results, we elected to study the simplest, most intuitive quantity, as in our previous work (Boettiger et al.,

2007; Boettiger et al., 2009). ICR values underwent an arcsine-square root transform – i.e. were variance-stabilized – to permit the application of parametric statistical tests.

Both before drug administration and after the scanner run, subjects completed a speeded responding task to assess potential changes in motor function on and off tolcapone. Subjects were required to make a button press response as soon as possible after the presentation of either a brief visual or auditory stimulus. Reaction times were compared both within each session and across the tolcapone and placebo conditions. Due to computer failures, these data were available for only 19 of our 23 subjects.

MRI image acquisition

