Resting state data were used to evaluate the connectivity between brain regions in both the tolcapone and placebo conditions in all subjects who completed both resting state sessions (N = 22; due to technical failures, complete resting state data from one of our 23 subjects were not obtained). This approach allowed us to identify any drug-related changes in connectivity independent of task performance. These data were smoothed by a 2.5mm FWHM Gaussian kernel prior to temporal bandpass filtering between 0.009 Hz and 0.08 Hz to reduce the influence of cardiac and respiratory artifact, per the protocol of Fox and colleagues (Fox et al., 2005). Movement parameters and the white matter and ventricular time series, but not the global mean signal, were included as regressors of no interest. A striatal region of interest in the left ventral putamen was chosen, based on the results of our univariate analyses (see Results, Figure 4a). A time course defined by averaging across voxels in this region was then correlated with every other voxel in the brain, and correlation coefficients were Fisher-transformed to allow for the application of parametric statistical tests. Images were then normalized to the MNI template

prior to the application of group-level statistics. Because of our hypotheses about changes in frontostriatal connectivity, data were masked with a prefrontal mask (AAL regions 3-32) before the appropriate cluster-size correction was calculated.

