For the evaluation of connectivity during task performance, we used the seed region (left ventral putamen) and significantly-connected region (left pregenual anterior cingulate cortex) identified in the resting state connectivity analysis shown in Figure 5b. For each of these two ROIs, the time series for each of the eight task-state runs was windowed with a 4-point split-cosine bell and concatenated with the other segments to produce a subject-specific time series. Time series within each ROI were then averaged across voxels to generate a single time series for each ROI. Coherency values were obtained by applying a fast Fourier transform (Matlab, <http://www.mathworks.com>) to the data for each pair of ROIs, implemented via Welch's periodogram averaging method using a 64-point discrete Fourier transform, Hanning window, and overlap of 32 points (Kayser et al., 2009). Coherence values for each ROI were then computed using the band-averaged coherence. To compute correlations between coherence results and other values, we first Fisher-transformed the coherence values to generate an approximately normal distribution (Rosenberg et al., 1989) that permitted us to apply parametric statistical tests.

Statistical Analysis

For analysis of behavioral data, paired T-tests and Pearson's correlation coefficients were used to calculate statistical significance. For univariate and multivariate analyses of BOLD data, significance was calculated using statistical techniques and corrections implemented in the Afni

software package, including the functions *3dDeconvolve*, *3dFWHMx*, *3dClustSim*, and *3dttest++*.

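### Adding visit order to the paired analysis of ICR, the primary behavioural outcome, is a cheap precision gain in this two-visit crossover (minor)

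*Combined protocol and SAP*

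**What the plan says.** The opening text on randomisation describes a two-period crossover: "Subjects were randomized in double-blind, counterbalanced, placebo-controlled fashion to either placebo or a single 200mg dose of tolcapone on their first visit", with the other treatment at the second visit. The choice task is done in the scanner after dosing. ICR in the Want condition is named as the primary behavioural outcome and is put on the arcsine-square-root scale for parametric testing. No pre-drug ICR is described.

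The Statistical Analysis section gives the behavioural method in one sentence: "For analysis of behavioral data, paired T-tests and Pearson's correlation coefficients were used to calculate statistical significance". For BOLD data it lists AFNI functions, including 3dttest++, and does not state the group-level model.

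Neither that section nor the sections on the task, the univariate analysis and the multivariate analysis names a visit, period, sequence or order term. None reports how many subjects had each order.

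**The concern.** Each subject's tolcapone-minus-placebo difference contains the drug effect plus or minus the difference between visits, with the sign set by the order received. Practice, familiarity with the scanner or a drift in preference could all produce such a difference. Counterbalancing largely cancels it from the mean of the differences but leaves it in their spread. A plain paired t-test treats that spread as noise. Because no pre-drug ICR is described, the randomised order is the available means of removing it.

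At stake is a missed or imprecisely estimated drug effect on ICR in a study of 23 subjects, if the visits did differ. A drug effect already detected is not undermined by lost power.

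**Working it through.** **Inputs from the documents.** Two-visit counterbalanced crossover; 23 subjects; paired t-test for behavioural data. The text states no sample-size or power figure, so there is none to reproduce.

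**Assumptions.** ICR available for all 23; order split 12/11 (nearest to even), with 14/9 as a sensitivity case; two-sided 5% test (the text gives 0.05 only for BOLD maps); drug effect τ = 0.6; visit effect π (visit 2 minus visit 1) of 0 to 0.5. Effects are in units of the within-order SD of the paired difference.

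**Model.** d = τ + sπ + e, with s = +1 if tolcapone came second, −1 if it came first, and e with SD 1.

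**Effect on the mean.** The unadjusted mean is shifted by π(n₁ − n₂)/n. At 12/11 this is π/23 = 0.043π, or 0.022 SD at π = 0.5.

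**Effect on the variance.** The expected sample variance of d is 1 + π²·4n₁n₂/[n(n − 1)]. At 12/11 the multiplier of π² is 528/506 = 1.0435.
- π = 0.25: variance 1.065, SD 1.032
- π = 0.50: variance 1.261, SD 1.123

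**Confidence interval half-width.**
- Unadjusted (22 df): 2.074 × SD/√23 = 0.446 at π = 0.25 and 0.486 at π = 0.5.
- Order-adjusted (21 df), using the mean of the two order-group means: 2.080 × √[¼(1/12 + 1/11)] = 2.080 × 0.2087 = 0.434 at any π.
- The unadjusted interval is therefore 2.8% wider at π = 0.25 and 11.9% wider at π = 0.5.

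**Power and type I error by simulation, 12/11, τ = 0.6.** In the favourable direction the one extra subject is in the order where the visit effect adds to the drug effect.

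| Visit effect | Unadjusted power, favourable / unfavourable | Average | Order-adjusted power | Unadjusted type I error |
|---|---|---|---|---|
| 0 | 0.785 | 0.785 | 0.783 | 0.050 |
| 0.1 | 0.788 / 0.776 | 0.782 | 0.783 | 0.049 |
| 0.25 | 0.781 / 0.750 | 0.766 | 0.783 | 0.044 |
| 0.5 | 0.740 / 0.673 | 0.71 | 0.783 | 0.030 |

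The average gain from adjusting is about 1.7 points at 0.25 SD and about 8 points at 0.5 SD. At a visit effect of 0.5 SD, a drug effect of 0.4 gives 0.40/0.32 unadjusted against 0.45 adjusted, and 0.8 gives 0.94/0.91 against 0.955.

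**Cost if visits do not differ (τ = 0.6).** Power goes from 0.785 to 0.783 at 12/11 and from 0.785 to 0.764 at 14/9.

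**Break-even, averaged over direction.** For a drug effect that gives 80% power with no visit effect (τ = 0.611), adjustment starts to gain at a visit effect of about 0.09 SD at 12/11 and about 0.23 SD at 14/9.

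**The case against.** The strongest reply is that nothing is shown to be wrong. Counterbalancing is the design's own protection against visit effects. The paired t-test with a near-even split does not exceed its nominal error rate, and nothing in the documents shows that visits differed. A loss of about 8 points needs a visit effect of 0.5 SD, almost as large as the assumed drug effect. All of this stands, and it limits the point to precision. It does not remove it, because the adjustment uses information already held and costs very little. It is also fair to say that part of the text and the Results were not available, and an order check may be there. If so, citing it settles the matter.

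A reader might infer more than the documents support:

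- **That the imaging analyses left order out.** The paired-test sentence covers behavioural data only, and the BOLD group model is not described. The text is silent there.
- **That the reaction-time comparison is biased by visit because four subjects were lost.** The text attributes the losses to computer failures and says nothing about their order. The task was also done before dosing at each visit: "Reaction times were compared both within each session and across the tolcapone and placebo conditions". A comparison of change from that measurement would remove a stable visit shift, and the text does not show that only post-drug values were compared.
- **That the coherence correlations are inflated by order.** That would need both variables to be tolcapone-minus-placebo changes that shift with visit. The text says only "To compute correlations between coherence results and other values, we first Fisher-transformed the coherence values" and does not describe change scores.
- **That adjustment pays only beyond some fixed visit effect, such as 0.25 SD.** The break-even moves with the order split, so no single threshold applies.

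**Conclusion.** The point holds as a minor improvement to the ICR analysis. The stated paired t-test is valid with a near-even split but gives away precision if visits differ. Under the assumptions above, the average loss is about 1.7 power points at a visit effect of 0.25 SD and about 8 at 0.5 SD, with type I error falling to 0.044 and 0.030. If visits do not differ, nothing is lost by omitting order.

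The visit effect, drug effect, order split and behavioural significance level are all assumed. The documents do not show which row of the table applies, and they do not support a reading that the ICR result is biased or invalid.

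**What to change.** - Analyse transformed ICR with drug and visit as fixed effects and subject as a random effect. Equivalently, regress the tolcapone-minus-placebo difference on order coded ±0.5, without mean-centring, and test the intercept.
- Report how many subjects had each order and the estimated visit effect.
- Keep the paired t-test as a sensitivity analysis.
- Enter the same order covariate in the group 3dttest++ drug contrasts if it is not already there, and state the group model.

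The analysis is reported as complete, so this is a rerun on existing data, with one covariate known for every subject and one degree of freedom spent. With an uneven split the plain test can reject more often when the visit effect happens to favour the drug, but part of that advantage is bias. The order term does not address carryover.

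### No adjustment for treatment order is described for the cross-subject correlations; if two drug-change measures both shift between visits, counterbalancing does not protect their correlation

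*Combined protocol and SAP*

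**What the plan says.** The opening description of the task states that subjects were "randomized in double-blind, counterbalanced, placebo-controlled fashion" and received one treatment "on their first visit and the alternative treatment on their second visit". Treatment order is therefore known for every subject. The number of subjects in each order is not given.

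Two places bear on correlations:

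- **Multivariate analysis, task-state connectivity.** Coherence is Fisher-transformed "To compute correlations between coherence results and other values". The partner values are not named. Nor does the text say whether changes between sessions, single-session values or averages over both sessions are correlated.
- **Statistical Analysis.** Paired t-tests and Pearson "correlation coefficients were used to calculate statistical significance". This sentence is limited to behavioural data. BOLD analyses are covered by the sentence after it, which refers to AFNI functions.

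No order, visit, period or sequence term, no partial correlation and no check for a visit effect is described. The nuisance regressors named for the resting-state data (movement, white matter and ventricular signal) act within a scan and do not address order.

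**The concern.** A subject's tolcapone-minus-placebo difference contains the visit effect with a minus sign if tolcapone came first and a plus sign if it came second. With near-equal order groups these contributions cancel in the mean, so the paired t-test is protected. They do not cancel in the covariance of two such differences: minus times minus and plus times plus are the same product, so both order groups push the covariance the same way.

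Suppose choice behaviour and frontostriatal coherence both drift from the first visit to the second, for example because the scanner and task have become familiar. Their drug-change scores would then correlate even if the drug's effects on the two were unrelated. If the drifts run in opposite directions, a real relation can be hidden or reversed. Either result could be misread as evidence about a link between drug-related brain change and drug-related choice change.

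**Working it through.** **Inputs from the documents.** There are 23 subjects in all ("these data were available for only 19 of our 23 subjects", said of the speeded-response task) and 22 with resting-state data ("N = 22; due to technical failures, complete resting state data from one of our 23 subjects were not obtained"). Each subject has one visit per treatment, in counterbalanced order. The plan states no figure for the power of a correlation or for a visit effect, so there is nothing of its own to reproduce.

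**Assumptions.** The order split is 12/11 for N = 23, the data are bivariate normal, and tests are two-sided at 5%. Visit shifts are expressed in within-order SDs of the change score.

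**Model.** For each measure, D = τ + sπ + e. Here τ is the mean drug effect, s = −1 if tolcapone came first and +1 if second, and π is the visit-2-minus-visit-1 shift. Let ρ be the within-order correlation and w = 4·n₁·n₂/n². The correlation pooled over both orders is

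r = (ρ + w·πₓ·π_y) / √[(1 + w·πₓ²)(1 + w·π_y²)].

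With 12/11, w = 4 × 12 × 11 / 23² = 528/529 = 0.998. With equal orders w = 1, so exact balance does not remove the product term.

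**Formula results.**

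- ρ = 0, both shifts 0.25: 0.0624/1.0624 = 0.06.
- ρ = 0, both shifts 0.5: 0.2495/1.2495 = 0.20.
- ρ = 0, both shifts 1.0: 0.998/1.998 = 0.50.
- ρ = 0.5, shifts +0.5 and −0.5: (0.5 − 0.2495)/1.2495 = 0.20.
- ρ = 0.5, a 0.5 shift in one measure only: 0.5/√1.2495 = 0.45.

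**Rejection rates by simulation** (at least 40,000 replicates per row, 12/11). Plain Pearson uses N − 2 degrees of freedom; the partial correlation given order uses N − 3.

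| True ρ | Shifts (SD) | Plain: mean r | Plain: rejects | Adjusted: rejects |
|---|---|---|---|---|
| 0 | 0, 0 | 0.00 | 5% | 5% |
| 0 | 0.25, 0.25 | 0.06 | 6% | 5% |
| 0 | 0.5, 0.5 | 0.21 | 15% | 5% |
| 0 | 0.8, 0.8 | 0.40 | 50% | 5% |
| 0 | 1.0, 1.0 | 0.51 | 77% | 5% |
| 0 | 0.5, 0 | 0.00 | 5% | 5% |
| 0.5 | 0, 0 | 0.49 | 71% | 69% |
| 0.5 | 0.5, 0.5 | 0.60 | 90% | 69% |
| 0.5 | 0.5, −0.5 | 0.18 | 12% | 69% |
| 0.5 | 0.5, 0 | 0.44 | 59% | 69% |

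Simulated means differ slightly from the formula because the formula is a large-sample value. An 11/11 split with N = 22 gives nearly the same picture: 15% at shifts of 0.5 and 75% at 1.0.

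**Other kinds of value.**

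- *Single-session values.* Centred on their mean, the two order groups differ by ±π/2, measured against the between-subject SD. A visit shift of 0.5 between-subject SD therefore corresponds to the 0.25 row (about 6%), and one of 1.0 SD to the 0.5 row (about 15%).
- *Averages over both visits.* Every subject carries the same π/2, so nothing is added to the covariance.
- *A partner measure not tied to a visit.* Its shift is zero, so the product is zero.

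**The case against.** The algebra is not in dispute; what can be disputed is whether its conditions are met. The documents never describe a correlation between drug-related brain change and drug-related choice change. The partner values for coherence are undefined and could be visit averages or measures unrelated to visits, where the problem does not arise. The larger error rates need substantial shifts in both measures, and no shift is documented. The task instructions and the 10 to 20 practice trials may reduce a practice effect, and the key condition records preference rather than skill. The only correlation with a reported value, 0.78 between the impulsive choice ratio and the discounting rate, compares two summaries of the same choices and is not seriously threatened.

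All of this stands as a limit on the point. It does not remove it, because the text leaves the vulnerable case open and counterbalancing is the only protection named.

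Three stronger readings are tempting and are not supported:

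- *That the correlations were not adjusted for order.* The documents are silent, and part of the text was not available; one can say only that no adjustment is described.
- *That a Pearson correlation is invalid in any crossover of this kind.* A shift in one measure alone leaves type I error at 5% and only attenuates a true correlation.
- *That the primary result is undermined.* The paired comparison of the impulsive choice ratio is protected by near-even counterbalancing and is not at issue here.

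**Conclusion.** The concern holds conditionally. Where tolcapone-minus-placebo changes in two measures are correlated and both measures shift between visits, an unadjusted Pearson correlation is biased by the product of the shifts, and balance between orders does not help. At equal shifts of 0.5 SD the nominal 5% test rejects about 15% of the time; opposite shifts of the same size cut power for a true r of 0.5 to 12%. A shift in one measure alone costs power only, and single-session values are less affected. These sizes rest on an assumed order split, normal data and assumed shifts. The bias in this trial cannot be estimated from the documents. The point is worth acting on because the safeguard is nearly free, but it bears on supporting brain-behaviour correlations only.

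**What to change.** State which values enter each cross-subject correlation: drug-minus-placebo changes, single-session values, or averages over both visits. Where changes or single-session values are used (coherence, connectivity or BOLD with the impulsive choice ratio or other session measures), report the partial correlation adjusted for whether tolcapone came first or second, tested on N − 3 degrees of freedom. Centring both measures within order group and correlating the residuals is equivalent. Base brain-behaviour conclusions on the adjusted value. Also report the number of subjects in each order and the observed visit effect on the impulsive choice ratio and on coherence, so that a reader can judge how much the adjustment matters.

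The cost is one degree of freedom and no new data. From r = t/√(df + t²), the critical |r| at N = 23 rises from 2.080/√(21 + 2.080²) = 0.413 to 2.086/√(20 + 2.086²) = 0.423; at N = 22 it rises from 0.423 to 0.433. With no visit effect, power at a true r of 0.5 and N = 23 falls from 71% to 69%.
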